### **9.2.2. Analysis of Secondary Endpoints**

For the key secondary endpoint of time to flare, descriptive statistics will include median time to flare and 95% confidence interval using the Kaplan-Meier approach. In addition an estimate of the relative flare rates in the current study and that seen in those subjects in protocol B1801031 who met the treatment withdrawal criteria for the current protocol will also be obtained; subjects in B1801031 did not discontinue treatment and will serve as a reference population. For this estimate a Cox Proportional Hazards model will be used. A 99% confidence interval will be calculated for the Hazard Ratio. Additional sensitivity analyses evaluating the impact of covariates may be performed, details will be provided in the statistical analysis plan.

The efficacy upon retreatment will be assessed descriptively as the proportion of subjects who achieve an ASDAS CRP inactive disease less than 1.3; this will be expressed as a percent with 95% confidence interval.

Dichotomous clinical and subject rated endpoints measured during Periods 1 and 2 will be summarized as number evaluated, percent with response of interest and 95% confidence intervals.

For continuous clinical and subject rated endpoints measured during Periods 1 and 2, both raw and change values will be summarized with the following descriptive statistics: n, mean, standard deviation, min and max, median and the 25th and 75th percentiles (quartiles).

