2. INTRODUCTION

The purpose of this document is to provide further details about the statistical analysis methods specified in study protocol B1801381.

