5.1. Hypotheses and Decision Rules

This study is an open-label study with one treatment group. Inferences will be based on point estimates and confidence intervals, rather than on hypothesis tests.

Except where stated, all confidence intervals will be 2-sided 95% confidence intervals.

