5.2.4. Analyses for Time to Event Data

Kaplan-Meier (KM) estimates, including plots, will be used to illustrate the time course of flare after treatment withdrawal. In addition to summarizing the data from the current study, the KM plots will show subjects from protocol B1801031 who met the entry requirements for the current trial withdrawal period. Those subjects did not have treatment withdrawn and will serve as a reference for evaluating the impact of treatment withdrawal. As a sensitivity analysis a life table approach will be used to compare the time to flare between the 2 studies, with time intervals based on visit windows.

In addition to the KM summaries, Cox proportional hazards models will be used to estimate the hazard ratio of continuing (B1801031) to withdrawn (B1801381) subjects.

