6. ANALYSES AND SUMMARIES

6.1. Primary Endpoint(s)

6.1.1. ASDAS flare

6.1.1.1. Primary Analysis

Endpoint: ASDAS flare (ASDAS ESR greater than or equal to 2.1).

- Analysis time points: Period 2 (over entire period).
- Analysis population: Period 2 FAS.
- method of imputation for missing data: LOCF.
- Primary analysis methodology: Descriptive summary only of proportion flared at each period 2 visit.

Reporting results:

- Descriptive: proportions (n/N) and 95% Confidence interval) at each period 2 visit.

- Supporting objective and Decision rule: Primary Objective.

Additional analyses for primary endpoint

- Method of imputation for missing data: None .
- Analysis methodology: Kaplan Meier estimate of time to flare and Cox proportional hazards model for evaluation of covariates and estimation of hazard compared to prior study B1801031 which had no withdrawal of treatment.
- Supporting objective and Decision rule: Primary Objective.
- Covariates used (Cox model): Covariates for the Cox regression model of time to flare will include, in addition to study (B1801031 vs B1801381), age, sex, geographic region, baseline CRP (normal vs. high), baseline MRI status (negative vs. Positive), disease duration, prior NSAID response (good vs. not) plus ASDAS values at weeks 12 and 24 or, in a separate model, sustained ASDAS inactive disease in period 1, defined as ASDAS ESR<1.3 at Week 12 or Week 16 (where ASDAS may not be greater than 2.1 at either time point) and at Week 24. Binary variables with small frequencies in either study will not be included in the Cox regression model.

Reporting results:

- Estimation:

Kaplan-Meier estimates of 25%, median and 75% survival and 95% confidence intervals.
Cox model based hazard ratio estimates for covariates and study.
- Tables: Present table with just HR and CI for “study” for 4 models:
 1. study only
 2. study plus baseline variables
 3. study plus baseline variables plus ASDAS continuous at 2 times
 4. study plus baseline variables plus sustained ASDAS remission
- Figures:

Kaplan Meir plots showing both studies flare events.

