6.4. Subset Analyses

In addition to summarization of the overall population, the ASDAS flare endpoint will be summarized for key demographic and baseline disease characteristics for the B1801381 population. For each demographic and disease characteristic subgroup, the response in each subgroup category will be presented (responder count, group size, and response percent). In addition Cox regression models with factors for study, subgroup and study by subgroup interaction will be fit, separately for each subgroup. Results will be summarized with hazard ratios and 95% confidence intervals. The subgroups to be included are:

- Sex (Male, Female)
- Race (White, Non-White)
- Age category (<40 years, >=40 years)

- Weight (<70kg, ≥70 kg)
- Baseline hs-CRP status (High, Normal)
- HLA-B27 status (Positive, Negative)
- Concomitant use of DMARDs at Baseline (Yes, No)
- MRI sacroiliitis classification at Screening (Positive, Negative)
- Both positive MRI and elevated baseline hs-CRP (Yes/No)
- Baseline/screening MRI SIJ SPARCC score >2 (yes, no)
- History of IBD at Screening (Yes, No)
- History of uveitis at Screening (Yes, No)
- Disease duration <2 years (Yes, No).

Before the final model is determined, data patterns will be examined for feasibility issues, including highly correlated predictors and small cell size in subgroups. Adjustments will be made as necessary to address any such issues.

To support the interpretation of the primary analysis the following analysis will be performed:

- Sustained period one responders vs. responders at week 24 only.

An additional summary evaluating flare rates in those subjects who met the entry criteria only at week 24 and those who were sustained responders [subjects who, in addition to ASDAS ESR <1.3 at week 24, also have ASDAS ESR <1.3 at Week 12 or Week 16 (where ASDAS may not be greater than 2.1 at either time point)] will be provided. Populations and methodology will be applied as above.

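### Does the gap between the protocol's 99% interval for the hazard ratio against B1801031 and the SAP's 95% default call for a change?

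*Protocol*

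**What the plan says.** Protocol 9.2.2 (Analysis of Secondary Endpoints) plans a Cox model comparing flare in this study with flare in those B1801031 subjects who met the present withdrawal criteria but stayed on treatment. For that ratio it states: "A 99% confidence interval will be calculated for the Hazard Ratio". The other intervals in the section (median time to flare, retreatment response, dichotomous endpoints) are at 95%.

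The SAP describes its purpose in section 2 as to "provide further details about the statistical analysis methods specified in study protocol". On this ratio it says in 5.2.4: "Cox proportional hazards models will be used to estimate the hazard ratio of continuing (B1801031) to withdrawn (B1801381) subjects". SAP 6.1.1.1 gives the reporting. For the survival curves it names a level: "Kaplan-Meier estimates of 25%, median and 75% survival and 95% confidence intervals". For the ratio it does not: the table entry begins "Present table with just HR and CI for" and goes on to the study term in four models. SAP 6.4, on subgroup Cox models that also contain a study factor, says: "Results will be summarized with hazard ratios and 95% confidence intervals". The general rule is in SAP 5.1: "Except where stated, all confidence intervals will be 2-sided 95% confidence intervals". No SAP section mentions 99%, and the SAP's table of changes records no change of level.

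On the label, the protocol summary, Protocol 2.2.2 and 9.2.2, and SAP 3.1 and 3.2 all make time to flare the key secondary endpoint. Protocol 9.1 attaches that label to retreatment response. SAP 4.2 mentions the primary and key secondary endpoints for an optional per-protocol set and puts ASDAS inactive disease and ASAS 40 in brackets after them.

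**The concern.** The study reports estimates, not tests. SAP 5.1 says "Inferences will be based on point estimates and confidence intervals, rather than on hypothesis tests", so the interval around the hazard ratio is the main expression of uncertainty for the secondary objective of comparing time to flare with B1801031. Protocol 9.2.2 singles out that one quantity for 99%, which looks deliberate. The SAP presents itself as adding detail to the protocol's methods, then leaves the level blank where it specifies the ratio, although it writes 95% for the Kaplan-Meier estimates in the same section. One analyst could apply the SAP default and another could keep the protocol's 99%. They would then publish intervals of different width from the same model, and the narrower one would look like an unexplained relaxation.

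The label raises a similar worry. If it is unclear which endpoint is key secondary, it may be unclear what the sample size supports and what a per-protocol analysis would cover.

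**Working it through.** **Which level applies.** Three provisions, read together, settle it.

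1. Protocol section 9 says the SAP may modify the analyses outlined in the protocol. Only major modifications of the primary endpoint definition or its analysis must also appear in a protocol amendment.
2. Protocol 9.2.2 treats the hazard ratio as a secondary analysis. The primary analysis is the flare proportion (Protocol 9.2.1).
3. SAP 5.1 sets two-sided 95% unless the SAP states otherwise, and it does not do so for this ratio.

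The SAP level is therefore 95%, and the protocol allows it. This is an unexplained difference between the documents. It is not a missing specification.

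**The plan's own precision figures.** Protocol 9.1 gives half-widths of about 10% for the flare rate (70% of 96) and about 12% for retreatment response (60% of those who flare). The half-width is z × √(p(1 − p)/n), and the number of flares is 0.70 × 96 = 67.2, taken as 67.

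| Quantity | p | n | 95% (z = 1.960) | 99% (z = 2.576) |
|---|---|---|---|---|
| Flare rate | 0.70 | 96 | 9.2% | 12.0% |
| Retreatment response | 0.60 | 67 | 11.7% | 15.4% |

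The stated figures match the 95% column. The sample size thus rests on 95% intervals for two proportions. It does not use the hazard ratio, so the level chosen for the ratio leaves the sample-size rationale untouched.

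**Size of the difference for the hazard ratio.** The limits are HR × exp(± z × SE), where SE is the standard error of log HR. The ratio of the two widths on the log scale does not depend on the data:

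- 2.576/1.960 = 1.314, so the 99% interval is 31% wider.
- 1.960/2.576 = 0.761, so the 95% interval is 24% narrower.

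The documents give no flare count for B1801031. As an illustration for the study-only model, take SE ≈ √(1/67 + 1/e), where e is an **assumed** number of flares in the comparator. Each limit is the estimate multiplied or divided by the factor shown.

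| e (assumed) | SE | 95% factor | 99% factor |
|---|---|---|---|
| 5 | 0.464 | 2.48 | 3.30 |
| 10 | 0.339 | 1.94 | 2.39 |
| 20 | 0.255 | 1.65 | 1.93 |
| 40 | 0.200 | 1.48 | 1.67 |

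**Conversion.** A reader given one interval can compute the other, because the 99% factor is the 95% factor raised to the power 1.314. For e = 10, ln(1.94) ≈ 0.664, 0.664 × 1.314 ≈ 0.873 and exp(0.873) ≈ 2.39, as in the table. No information is lost at either level.

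**The label.** Five places (the protocol summary, Protocol 2.2.2 and 9.2.2, SAP 3.1 and 3.2) give it to time to flare. Protocol 9.1 alone gives it to retreatment response. The analyses of both endpoints are specified whatever they are called: Kaplan-Meier and Cox for time to flare, and a proportion with a 95% interval for retreatment response. The bracket in SAP 4.2 need not exclude flare. It can be read as explaining only the key secondary part, and SAP 6.1.1.1 places the time-to-flare analyses under the primary endpoint. The per-protocol set is optional.

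**The case for a change.** The strongest case for a change is that the protocol chose 99% for this one quantity, and nothing shows that the SAP meant to drop it. The SAP says it elaborates the protocol's methods, and its change table is silent. Where inference rests on intervals, their width is part of the result. If the estimate lay between the two factors in the table (for e = 10, between 1.94-fold and 2.39-fold away from 1), the 95% interval would exclude 1 and the 99% interval would not. A cross-study comparison may also be a place where extra caution was wanted. A phrase in SAP 6.1.1.1 would remove the doubt at almost no cost.

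Part of this stands. The departure is neither flagged nor explained, and a line of reason would be tidier. The rest carries less weight. The plan attaches no test, threshold or claim to whether the interval excludes 1. The documents give no rationale for 99%, so 95% cannot be shown to fall short of a stated aim. Neither level allows for differences between two studies whose subjects were not randomised against each other; a larger multiplier widens the interval but does not address that bias. The added line would record a choice without improving the estimate, its precision or its validity.

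Relabelling Protocol 9.1 would also need care. The same paragraph says the sample size rests on the primary and key secondary endpoints, yet it gives no precision figure for time to flare. Changing only the label would leave that sentence without its second calculation.

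**Conclusion.** No change to the plan follows. Protocol 9.2.2 says 99% and SAP 5.1 leads to two-sided 95%. Protocol section 9 permits the SAP's choice, and an analyst following the SAP obtains a valid interval. The effect is confined to reported width, a factor of 1.314 on the log scale whatever the data. The hazard ratio, its standard error, the Kaplan-Meier and life-table comparisons and the sample size are unaffected, and either interval can be derived from the other. The limits shown for specific event counts rest on 67 flares in this study (70% of 96), on assumed comparator counts of 5 to 40 and on an approximate standard error for the study-only model. The conclusion does not depend on them.

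The misplaced key secondary label in Protocol 9.1 is a clerical slip. In a study without hypothesis tests the label carries no inferential weight, and both endpoints have specified analyses. The SAP 4.2 bracket would matter only if the optional per-protocol analysis were run, and even then it can be read as covering flare under the primary endpoint.

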### **9.3. Safety Analysis**

The safety data will be summarized in accordance with Pfizer data standards. The safety analysis set will include all randomized subjects who have taken at least one dose of investigational product.

Listings and summary tabulations of AEs and treatment-emergent AEs will be generated. AEs will be classified by body system and preferred term and summaries of the number of subjects with events will be provided for each treatment group.

Listings and summary tables will be produced for vital signs (sitting blood pressure and pulse rate), weight, laboratory evaluations (hematology, blood chemistry, and urinalysis).

### **9.4. Interim Analysis**

Descriptive analyses of Period 1 will be performed when all subject data for Period 1 is complete. No interim analysis with the aim of stopping or modifying the trial in any way is planned.

### **9.5. Data Monitoring Committee**

This study will not use a data monitoring committee.

## **10. QUALITY CONTROL AND QUALITY ASSURANCE**

Pfizer or its agent will conduct periodic monitoring visits during study conduct to ensure that the protocol and Good Clinical Practices (GCPs) are being followed. The monitors may review source documents to confirm that the data recorded on CRFs are accurate. The investigator and institution will allow Pfizer monitors/auditors or its agents and appropriate regulatory authorities direct access to source documents to perform this verification. This verification may also occur after study completion.

During study conduct and/or after study completion, the study site may be subject to review by the IRB/EC, and/or to quality assurance audits performed by Pfizer, or companies working with or on behalf of Pfizer, and/or to inspection by appropriate regulatory authorities.

The investigator(s) will notify Pfizer or its agents immediately of any regulatory inspection notification in relation to the study. Furthermore, the investigator will cooperate with Pfizer or its agents to prepare the study site for the inspection and will allow Pfizer or its agent, whenever feasible, to be present during the inspection. The investigator will promptly provide copies of the inspection findings to Pfizer or its agent. Before response submission to the regulatory authorities, the investigator will provide Pfizer or its agents with an opportunity to review and comment on responses to any such findings.

It is important that the investigator(s) and their relevant personnel are available during the monitoring visits and possible audits or inspections and that sufficient time is devoted to the process.

## **11. DATA HANDLING AND RECORD KEEPING**

### **11.1. Case Report Forms/Electronic Data Record**

As used in this protocol, the term CRF should be understood to refer to either a paper form or an electronic data record or both, depending on the data collection method used in this study.

A CRF is required and should be completed for each included subject. The completed original CRFs are the sole property of Pfizer and should not be made available in any form to third parties, except for authorized representatives of Pfizer or appropriate regulatory authorities, without written permission from Pfizer.

The investigator has ultimate responsibility for the collection and reporting of all clinical, safety, and laboratory data entered on the CRFs and any other data collection forms (source documents) and ensuring that they are accurate, authentic/original, attributable, complete, consistent, legible, timely (contemporaneous), enduring, and available when required. The CRFs must be signed by the investigator or by an authorized staff member to attest that the data contained on the CRFs are true. Any corrections to entries made in the CRFs or source documents must be dated, initialed, and explained (if necessary) and should not obscure the original entry.

In most cases, the source documents are the hospital's or the physician's subject chart. In these cases, data collected on the CRFs must match the data in those charts.

In some cases, the CRF, or part of the CRF, may also serve as source documents. In these cases, a document should be available at the investigative site as well as at Pfizer and clearly identify those data that will be recorded in the CRF, and for which the CRF will stand as the source document.

### **11.2. Record Retention**

To enable evaluations and/or audits from regulatory authorities or Pfizer, the investigator agrees to keep records, including the identity of all participating subjects (sufficient information to link records, eg, CRFs and hospital records), all original signed informed consent documents, copies of all CRFs, safety reporting forms, source documents, and detailed records of treatment disposition, and adequate documentation of relevant correspondence (eg, letters, meeting minutes, and telephone call reports). The records should be retained by the investigator according to the ICH guidelines, according to local regulations, or as specified in the clinical study agreement (CSA), whichever is longer.

If the investigator becomes unable for any reason to continue to retain study records for the required period (eg, retirement, relocation), Pfizer should be prospectively notified. The study records must be transferred to a designee acceptable to Pfizer, such as another investigator, another institution, or an independent third party arranged by Pfizer. Investigator records must be kept for a minimum of 15 years after completion or discontinuation of the study or for longer if required by applicable local regulations.

The investigator must obtain Pfizer's written permission before disposing of any records, even if retention requirements have been met.

## **12. ETHICS**

### **12.1. Institutional Review Board/Ethics Committee**

It is the responsibility of the investigator to have prospective approval of the study protocol, protocol amendments, informed consent documents, and other relevant documents, eg, recruitment advertisements, if applicable, from the IRB/EC. All correspondence with the IRB/EC should be retained in the investigator file. Copies of IRB/EC approvals should be forwarded to Pfizer.

The only circumstance in which an amendment may be initiated prior to IRB/EC approval is where the change is necessary to eliminate apparent immediate hazards to the subjects. In that event, the investigator must notify the IRB/EC and Pfizer in writing immediately after the implementation.

### **12.2. Ethical Conduct of the Study**

The study will be conducted in accordance with legal and regulatory requirements, as well as the general principles set forth in the International Ethical Guidelines for Biomedical Research Involving Human Subjects (Council for International Organizations of Medical Sciences 2002), Guidelines for GCP (ICH 1996), and the Declaration of Helsinki (World Medical Association 1996 & 2008).

In addition, the study will be conducted in accordance with the protocol, the ICH guideline on GCP, and applicable local regulatory requirements and laws.

### **12.3. Subject Information and Consent**

All parties will ensure protection of subject personal data and will not include subject names or other identifiable data in any reports, publications, or other disclosures, except where required by law.

When study data are compiled for transfer to Pfizer and other authorized parties, subject names, addresses, and other identifiable data will be replaced by a numerical code based on a numbering system provided by Pfizer in order to de-identify study subjects. The study site will maintain a confidential list of subjects who participated in the study, linking each subject's numerical code to his or her actual identity. In case of data transfer, Pfizer will maintain high standards of confidentiality and protection of subjects' personal data consistent with applicable privacy laws.

The informed consent documents must be in compliance with ICH GCP, local regulatory requirements, and legal requirements, including applicable privacy laws.

The informed consent documents used during the informed consent process must be reviewed and approved by the sponsor, approved by the IRB/EC before use, and available for inspection.

The investigator must ensure that each study subject is fully informed about the nature and objectives of the study and possible risks associated with participation.

The investigator, or a person designated by the investigator, will obtain written informed consent from each subject before any study-specific activity is performed. The investigator will retain the original of each subject's signed consent document.

